4.0 Treatment Plan

4.1 The investigational agent for this study is Pacritinib.

- 4.1.1 Patients will start Pacritinib 200 mg po bid.
- 4.1.2 Patients can proceed to transplant after 60 days of starting Pacritinib but not more than 180 days.
- 4.1.3 Pacritinib will be stopped 21 days prior to starting preparative regimen for SOC Allo TP.
- 4.1.4 If for whatever reason a patient cannot pursue or receive SOC Allo TP, they will be able to continue treatment with Pacritinib until there is evidence of disease progression.
- 4.1.5 A patient will still be able to proceed to SOC ALLO TP if for any reason they cannot complete 60 days of treatment prior to transplant.
- 4.1.6 If a patient vomits or misses a dose, will continue treatment with the next scheduled dose. Missed doses and reason for non-compliance will be recorded.
- 4.1.7 Every effort should be made to avoid CYP3A4 inducers or inhibitors (see Appendix H) while patients are on pacritinib. If concomitant therapy with CYPsA4 inhibitors or inducers is medically necessary and there are no available or suitable substitutes, this should be documented in the patient's medical record and extreme caution taken with their continued use during the study duration.
- 4.1.8 Patients will document compliance of taking medication on a patient diary.

4.2 Treatment Interruption:

Safety parameters including AEs, hematology, and serum chemistry will be monitored according to the protocol. Pacritinib treatment may be withheld for up to 4 weeks due to drug-related toxicities. A longer recovery period may be allowed based on the toxicity, but must be agreed upon between the investigator and medical monitor. After treatment interruption, patients may resume the pacritinib treatment at the same dose level or at a reduced dose level. No dose re-escalation is allowed.

4.3 Pacritinib Dose Management Guidelines for Pacritinib-Related Nonhematologic Toxicities:

- 4.3.1 A maximum of 2 dose reductions is allowed. The first dose reduction will be a 100 mg reduction from the original dose. The dose will be reduced to 200 mg Q AM and 100 mg Q PM
- 4.3.2 The second dose reduction will be another 100 mg reduction and the dose will be reduced to 100 mg BID.
- 4.3.3 Once the dose is reduced, no re-escalation is allowed.
- 4.3.4 Dose management for nonhematologic toxicities is summarized in Table 3.

Table 3 Treatment Toxicity and Dose Management: Pacritinib-Related Nonhematologic Toxicities		

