SOC transplant conditioning with Fludarabine and Busulfan AUC of 4000 microMol-min per day providing that pharmacokinetic can be done, otherwise Busulfan dose will be given as a fixed dose of 100 mg/m² daily for four days. A SOC treatment plan and informed consent will be used for this.

4.7 GVHD Prophylaxis and Supportive Care as per standard practice in patients receiving allogeneic transplant:

Recipients of matched related and unrelated donors will receive tacrolimus and Mini Methotrexate as per institutional standard.

Recipients of matched or one antigen mismatched unrelated donors will receive anti thymocyte globulin (ATG) tacrolimus and Mini Methotrexate as per institutional standard. Patients who do not have a suitable related or unrelated donor and who are going to undergo transplant from a haploidentical donor will come off study.

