6.0 Statistical Considerations

General

This will be a single-arm, Phase II study of pacritinib, fludarabine, and busulfan as a preparative

regimen in allogeneic stem cell transplantation in patients with myelofibrosis. The primary endpoint is progression-free survival (PFS) in patients undergoing matched related or at least 7/8 matched unrelated donor transplant. We will enroll at least 21 evaluable patients, defined as patients who undergo transplant with a matched related or at least 7/8 matched unrelated donor. Patients who do not have a suitable related or unrelated donor will come off study and may receive a transplant from a haploidentical donor. For this reason and because some patients may decide not to undergo transplant after starting the drug, we may need to enroll up to 40 patients to ensure that 21 are evaluable for our primary endpoint.

Endpoints

6.1 Primary End Point (Progression-Free Survival):

Progression-free survival is defined as the time of stem-cell transplant to the time of death or disease progression.

6.2 Secondary End Points:

Neutrophil Engraftment is defined as a sustained ANC \geq 0.5 x 10 $^{\circ}$ /L for 3 consecutive days and evidence of donor chimerism by D+28 (the first chimerism study will be done 3-4 weeks post-transplant).

Platelet Engraftment is defined as a sustained first of three consecutive laboratory values of platelet $\geq 20x109/L$ with no platelet transfusions administered for 7 consecutive days.

Non-relapse mortality is defined as death without disease progression.

Liver response will be defined by the change in the size of the liver measured below the coastal margin in the mid-clavicular line by palpitation.

Spleen response will be defined by the change in the size of the spleen measured below the coastal margin in the mid-clavicular line by palpitation.

Quality of life will be measured by the QOL FACT BMT.

Symptom score will be measured by the MPD symptom score.

Immune recovery will be measured by various cell subsets and cytokine levels.

Primary Graft Failure is defined as failure to achieve an ANC \geq 0.5 x 10 $^{\circ}$ /L for 3 consecutive days by day 28, with <10% cellularity on bone marrow biopsy and no evidence of donor chimerism.

Secondary graft failure is defined as a sustained declined of ANC <0.5 x 10°/L for 3 consecutive days after initial documented engraftment with no evidence of disease progression.

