We will use descriptive statistical methods to tabulate safety parameters such as the rate of adverse events. Only patients who undergo transplant with a matched related or at least 7/8 matched unrelated donor will be include in these analyses.

We will separately summarize safety and other data for patients who receive pacritinib but who do not undergo stem cell transplant.

We will perform a descriptive statistical analysis of the Participant Follow-up Assessment questionnaire (Global Impression of Change Scale, Appendix F.) data collected at approximately 1, 3, 6, and 12 months post-transplant.

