8.0 Adverse Events and Reporting Requirements

8.1 AEs during Pacritinib phase

The severity of the adverse events (AEs) will be graded according to the Common Terminology Criteria v4.0 (CTCAE). We will not capture expected Grade 1 and Grade 2 AEs. Grade 3 and 4 AEs will be collected and recorded in the medical record. Only Pacritinib-related adverse events and protocol specific data will be entered into PDMS/CORe. PDMS/CORE will be used as the electronic case report form for this protocol.

Events not included in the CTCAE chart will be scored as follows: General grading:

Grade 2: Moderate: discomfort present with some disruption of daily activity, require treatment.

Grade 3: Severe: discomfort that interrupts normal daily activity, not responding to first line treatment.

Grade 4: Life Threatening: discomfort that represents immediate risk of death

Causality Assessment

For the purpose of this study, events known to be caused by Pacritinib will be assessed as definitely related.

Events known to be caused by components of the transplant package and its direct consequences as well as those events known to be related to drugs used for the treatment of GVHD, infections and supportive treatment will be scored as unrelated.

When the relationship of the adverse event cannot be ruled out with certainty the AE may be considered possibly related.

The PI will be responsible for assessing the causality and will be final arbiter. Documentation of grade, onset/resolution date and attribution will be entered into the patient's medical record and signed by the PI.

Collection of adverse events

Collection of adverse events will reflect the onset and resolution date and maximum grade. Intermittent events should be labeled as such and followed until resolution. If a patient is taken off study while an event still ongoing, this will be followed until resolution unless another therapy is initiated. Pre-existing medical conditions will be recorded only if an exacerbation occurs during the active treatment period. Co-morbid events will not be scored separately.

Adverse events related to Pacritinib will be collected and recorded for the duration of active treatment plus 14 days.

List of expected adverse events related to Pacritinib: Occurring in >10% include:

1. Nausea, vomiting, diarrhea, dehydration

- 2. Anemia, thrombocytopenia
- 3. Fatique

Treatment Duration Definitions:

Active Treatment: patients receiving Pacritinib.

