All life-threatening or fatal events, that are unexpected, and related to the study drug, must have a written report submitted within **24 hours** (next working day) of knowledge of the event to the Safety Project Manager in the IND Office.

The investigator will inform CTI Biopharma of any SAE within 24 hours of being aware of the event via email and/or fax.

Unless otherwise noted, the electronic SAE application (eSAE) will be utilized for safety reporting to the IND Office and MDACC IRB.

Serious adverse events will be captured from the time of the first protocol-specific intervention, until 14 days after the last dose of drug, unless the participant withdraws consent. Serious adverse events must be followed until clinical recovery is complete and laboratory tests have returned to baseline, progression of the event has stabilized, or there has been acceptable resolution of the event.

Additionally, any serious adverse events that occur after the 14 day time period that are related to the study treatment must be reported to the IND Office. This may include the development of a secondary malignancy.

Reporting to FDA:

Serious adverse events will be forwarded to FDA by the IND Sponsor (Safety Project Manager IND Office) according to 21 CFR 312.32.

Adverse events known to be related to SOC ALLO TP will not be recorded in PDMS.

List of most common expected adverse events related to SOC ALLO TP:

- 1. Infections in the presence or absence of neutropenia: fungal, bacterial and or viral infections.
- 2. Fever: Non-neutropenic or neutropenic without infection
- 3. Acute graft versus host disease (aGVHD): most commonly manifested by skin rash, diarrhea and abnormal liver function tests could also present with some degree of fever, upper gastrointestinal symptoms (nausea and vomiting) mucositis and eye dryness.
- 4. Gastrointestinal (GI tract): the GI tract manifestations could be not only due
- 5. to direct damage from the preparative regiment but also be a manifestation of GVHD or infections. Therefore, the time course and its presentation are crucial when assessing these as adverse events. Nausea/vomiting, mucositis, diarrhea when presented within first 7 to 10 days most likely will be related to the preparative regimen.
- 6. Skin rash: not related to GVHD could be caused by chemotherapy used for the preparative regimen or antibiotics used a supportive treatment.
- 7. Transaminitis: liver function test elevation.

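### Pacritinib adverse events are tabulated only in patients who go on to a matched-donor transplant; no all-treated rate is planned, and haploidentical recipients, read literally, are in neither safety summary

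*Combined protocol and SAP*

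**What the plan says.** - **Who is in the adverse event table.** After announcing a descriptive tabulation of safety parameters, including adverse event rates, Section 6.0 (Secondary Analyses) states: "Only patients who undergo transplant with a matched related or at least 7/8 matched unrelated donor will be include in these analyses".
- **Who is in the second summary.** The next paragraph adds: "We will separately summarize safety and other data for patients who receive pacritinib but who do not undergo stem cell transplant".
- **Which events are in the database.** Section 8.1: "Only Pacritinib-related adverse events and protocol specific data will be entered into PDMS/CORe". Later in Section 8.0, after the paragraph on reporting to FDA: "Adverse events known to be related to SOC ALLO TP will not be recorded in PDMS".
- **When events are collected.** Section 8.1: "Adverse events related to Pacritinib will be collected and recorded for the duration of active treatment plus 14 days". Section 4.1.3: "Pacritinib will be stopped 21 days prior to starting preparative regimen for SOC Allo TP".
- **Patients without a matched donor.** Section 6.0 (General): "Patients who do not have a suitable related or unrelated donor will come off study and may receive a transplant from a haploidentical donor". Section 4.7 says the same of those "who are going to undergo transplant from a haploidentical donor will come off study", and Section 7.6 lists the lack of such a donor as a reason for removal.
- **Numbers.** Section 6.0 (General) wants at least 21 evaluable patients, meaning recipients of a matched related or at least 7/8 matched unrelated transplant, and allows up to 40 to be enrolled to get them. It names two causes of the loss: haploidentical transplants and patients who decide against transplant after starting the drug.

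**The concern.** Pacritinib is the investigational agent (Section 4.1), and safety is part of the secondary objectives. Restricting the analysis to matched-donor recipients suits PFS, which starts at transplant. It does not suit drug toxicity, which is observed before transplant in every patient dosed. The main table would count drug-phase events only in patients who later met a condition unrelated to exposure.

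There are two consequences. First, the plan yields two summaries on different subsets and no rate for everyone exposed. Second, the two subsets do not cover all treated patients. A patient who takes pacritinib, leaves the study and receives a haploidentical transplant has not had a matched-donor transplant, so is outside the first summary. The patient has undergone a stem cell transplant, so on the wording is outside the second as well. Adding the two summaries restores the total only if these patients are assigned to one of them, and the text does not assign them.

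**Working it through.** **The plan's own figure.** The only design number involved is 21, the minimum denominator of the table. It comes from 1-year PFS of 61% against 80%, one-sided 5% error, 80% power, 3 years of accrual and 1 further year of follow-up.

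- Hazards: −ln 0.61 = 0.4943 and −ln 0.80 = 0.2231. Event probabilities under uniform accrual: 0.682 and 0.417.
- Hazard-scale formula: N = [z(0.95)·0.4943/√0.682 + z(0.80)·0.2231/√0.417]² / (0.4943 − 0.2231)² = 22.1, rounded up to 23.
- The cube-root scale gives 18.3, rounded up to 19. Simulated power at n = 21 is 0.82 to 0.86 depending on the form of the test.

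So 21 is reasonable, and nothing below depends on how it was derived.

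**Timing.** Routine collection ends at last dose + 14 days, and conditioning starts at last dose + 21 days. Gap: 21 − 14 = 7 days. On the protocol's own schedule, routine collection is over before the transplant that decides who is counted.

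**Share of dosed patients outside the main table**, (dosed − evaluable)/dosed:

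| Dosed | Evaluable | Outside | Share |
|---|---|---|---|
| 25 | 21 | 4 | 16% |
| 30 | 21 | 9 | 30% |
| 35 | 21 | 14 | 40% |
| 40 | 21 | 19 | 47.5% |
| 40 | 30 | 10 | 25% |

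The numbers dosed are assumptions, except that 40 is the stated enrolment maximum. The 47.5% is a ceiling: it needs 40 enrolled, all dosed, and only 21 evaluable.

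**Patients in neither summary.** The documents do not give the number of haploidentical recipients. Each one left unassigned leaves 1/40 = 2.5 percentage points of the all-treated rate undetermined with 40 dosed, or 1/25 = 4 points with 25 dosed.

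**Precision.** With no event observed, the one-sided 95% upper bound on an event rate is 1 − 0.05^(1/n): 13.3% at n = 21 and 7.2% at n = 40. The chance of seeing at least one case of an event with a true rate of 5% (assumed) is 1 − 0.95^n: 66% at n = 21 and 87% at n = 40.

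**Exposure.** Before transplant, the longest time on drug under Sections 4.1.2 and 4.1.3 is 180 − 21 = 159 days if the 180-day limit runs to the start of conditioning, or 180 days if it is read as time on drug. Section 4.1.4 lets patients who cannot have the transplant continue until progression, with no numeric limit. Exposure can therefore differ between the groups.

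**What the documents do not show.** Nothing says that toxicity decides who is transplanted. Section 7.1 takes patients off study for unacceptable toxicity but does not bar transplant, and Section 4.1.5 allows transplant after less than 60 days of drug. A direction of bias cannot be inferred.

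**The case against.** The usual harm of a restricted safety set is that treated dropouts disappear. Here the plan undertakes to report them: "We will separately summarize safety and other data for patients who receive pacritinib but who do not undergo stem cell transplant". Both summaries are descriptive, no test rests on them, and their counts can be added. The 16% to 47.5% is the share outside the first table, not the share missing from safety reporting. The haploidentical gap depends on a literal reading: these patients come off study, so the authors may have meant no transplant on study, which would place them in the second summary. Collection is not at risk either. Section 8.0 follows events still ongoing when a patient goes off study until resolution, unless another therapy is started. It also captures serious events to 14 days after the last dose unless consent is withdrawn.

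Much of this stands. The second summary softens the problem, the gap lies in the planned summaries rather than in the data, and a few words could settle where haploidentical recipients belong. Two things remain. The text does not contain those words, although Section 6.0 gives haploidentical transplant as one of the two reasons for over-enrolling. And even with them, no rate over all exposed patients is specified for the investigational drug, while the main table still conditions on an event that follows the collection window.

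**Conclusion.** The concern holds. The adverse event table describes drug-phase safety in a subset fixed by later matched-donor transplant. No all-treated rate is planned, and on a literal reading haploidentical recipients are in neither summary.

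With 21 evaluable, 16% of dosed patients are outside the main table if 25 are dosed and 47.5% at the ceiling of 40. Some of them are covered by the second summary; how many is unknown. Each haploidentical recipient left unassigned is worth 2.5 points of the all-treated rate with 40 dosed and 4 points with 25.

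The conclusion rests on the protocol's drug-stop and collection schedule being followed and on the stated enrolment figures. It makes no claim about the direction or size of bias. This should be corrected before analysis, but it does not threaten the primary result.

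**What to change.** - Define an all-treated safety set: every patient who takes at least one dose of pacritinib, whatever the later transplant status or donor type.
- Tabulate pacritinib-phase adverse events on that set, overall and in three subgroups: matched related or at least 7/8 unrelated transplant, haploidentical transplant, and no transplant.
- Report time on drug in each subgroup, since exposure may differ.
- Keep the matched-donor transplant set for PFS and the other transplant outcomes.
- For clarity, state that the 14-day collection window is completed for patients removed under Section 7.6. Section 8.0 already largely implies this.

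The cost is a change of wording in Section 6.0 and one extra table. Section 8.1 ties collection to dosing, not donor type, so no new data are needed. N = 21 and the PFS test do not change. The drawbacks are mixed exposure times in the pooled rate, which the time-on-drug column addresses, and small subgroups.

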Myelofibrosis results in extramedullary hematopoiesis, massive hepatosplenomegaly and fibrosis in the marrow and there are several major issues unique to it from transplant perspective. These include high incidence of graft failure and weak graft after transplant necessitating use of stem cell boost²² and organ dysfunction - particularly involving liver - leading to a high incidence of veno-occlusive disease and non-relapse mortality.⁴⁰ A safe agent that can reduce organomegaly and disease burden pretransplant may improve transplant outcome by improving engraftment, reducing organ toxicity and lowering relapse risk. Furthermore, it may allow more patients to become eligible for transplant by improving their performance status. A Jak 2 inhibitor might be the answer.

Jak 2 inhibitors and stem cell transplantation:

Discovery of Jak2 V617F mutation, which makes kinase constitutionally active in patients with myeloproliferative disorders led to development several targeted agents including Pacritinib to inhibit this pathway. Jak 2 is mutated in up 60% of patients with ET and MF and 98% of patients with PV. Even in patients without this mutation, this pathway is overactive. Ruxolitinib, a Jak2 inhibitor, is licensed by FDA for MF reduces splenomegaly, improves constitutional symptoms, and improves survival both in patients with and without Jak 2 V617F. Early data on its usage pre-transplant are conflicting with excellent outcome reported in some studies, but a possible higher complication rate reported in other study. This later study presented as an abstract is difficult to interpret, because complications reported are hard to differentiate from usual complications seen post-transplant. Pacritinib causes less myelosuppression than Ruxolitinib and may be superior to ruxolitinib as a pre-transplant agent to reduce organomegaly and to reduce the disease burden.

Pacritinib:

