5.0 Evaluation During Study

5.1 Disease Assessment Prior to Start of Pacritinib (baseline):

- a) Patient medical history and physical examination including measurement of liver and spleen size by physical examination or imaging (MRI or CT or ultrasound if possible) with addition of marrow-specific MRI sequences.
- b) CBC, differential and platelet count
- c) Bone marrow aspiration and biopsy
- d) Chemistry panel
- e) Serology for CMV, HBV, HCV and HIV
- f) B-HCG in women of childbearing potential
- g) 2 D echo, EKG
- i) Pulmonary function tests with DLCO
- j) Chest x-ray
- k) MF symptoms questionnaire (Appendix D.)
- I) Fact BMT questionnaire (Appendix E.)
- m) Blood for immunological profile if patient agrees to consent to optional study.

5.2 Follow up each month while on Pacritinib:

Patients will come to MDACC once each month to pick-up the next month's Pacritinib and have the following done. The monthly visits will continue as long as patient is taking Pacritinib.

- a) Medical history and physical examination
- b) CBC, differential and platelet count
- c) Chemistry panel
- d) EKG

Cycle 1 only: Day 14 (+/- 2 days) CBC, differential and platelet count and chemistry panel. These can be drawn locally and results sent to MDACC. The PI/treating physician must review outside lab results, determine clinical significance, sign and date the outside lab results.

Cycle 1 only: During week 2, study personnel will call patient about any new symptoms.

Patients treated on this protocol may require supportive care treatment (concomitant medications). These medications are considered standard of care and have no scientific contribution to the protocol; therefore no data will be captured on various medications needed or their side effects.

5.3 Within about 7 days after completion of Pacritinib (but before transplant):

- 1) Physical examination including measurement of liver and spleen size by physical examination or imaging (MRI or CT or ultrasound if possible).
- 2) EKG
- 3) Bone marrow aspiration and biopsy

5.4 Post-transplant Evaluations:

- 5.4.1 Post-transplant evaluations will follow our standard practice and are done to monitor engraftment and disease status.
- 5.4.2 Additional post-transplant follow-up specific to this study at approximately 1, 3, 6, and 12 months post-transplant:
 - 1) At around 3 months:
 - Measurement of liver and spleen size by physical examination or imaging (MRI or CT or ultrasound if possible).

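### Liver and spleen response to pacritinib is measured before transplant, but on the more natural reading of 6.0 it is analysed only in patients who later receive a matched transplant

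*Combined protocol and SAP*

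**What the plan says.** Section 1.0 lists liver and spleen response to pacritinib as secondary objective 1.4. Section 6.2 defines each response as a change in palpated organ size, and Secondary Analyses adds imaging. Neither gives a cut-off for a responder.

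Organ size is named at baseline (5.1) and again at 5.3, timed "Within about 7 days after completion of Pacritinib (but before transplant". The monthly on-drug visit in 5.2 has a physical examination but does not name organ size. Pacritinib stops 21 days before conditioning (4.1.3). A patient who cannot go to transplant may stay on it: "they will be able to continue treatment with Pacritinib until there is evidence of disease progression" (4.1.4).

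On numbers, 6.0 states: "We will enroll at least 21 evaluable patients, defined as patients who undergo transplant with a matched related or at least 7/8 matched unrelated donor". It adds that "we may need to enroll up to 40 patients to ensure that 21 are evaluable for our primary endpoint". Two reasons are given for the gap. One is a patient's decision against transplant after starting the drug. The other is the lack of a donor: "Patients who do not have a suitable related or unrelated donor will come off study and may receive a transplant from a haploidentical donor".

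Secondary Analyses ends with the restriction "Only patients who undergo transplant with a matched related or at least 7/8 matched unrelated donor will be include in these analyses", followed by: "We will separately summarize safety and other data for patients who receive pacritinib but who do not undergo stem cell transplant".

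**The concern.** The organ response is complete before the transplant takes place, and donor type cannot alter it. Restricting its analysis to matched-transplant recipients therefore selects patients on something that happens after the outcome is measured. If reaching a matched transplant is related to response, the estimate in that subset is not the estimate for patients given pacritinib, which is what objective 1.4 asks for. Section 2.0 itself allows for such a link, saying of a pre-transplant agent that reduces organ size and disease burden that "it may allow more patients to become eligible for transplant by improving their performance status".

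At stake is the interpretation of one descriptive secondary endpoint, the most direct measure in this trial of what pacritinib does before transplant.

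**Working it through.** **1. The plan's figure of 21.** Inputs from 6.0: 1-year PFS 61% against 80%, 3 years of accrual, 1 further year of follow-up, one-sided 5% test, 80% power. Accrual is assumed uniform.
- Hazards: −ln 0.61 = 0.4943 and −ln 0.80 = 0.2231.
- Event probability p = 1 − (e^(−λ) − e^(−4λ))/(3λ): 0.682 and 0.417.
- n = [1.645 × 0.4943/√0.682 + 0.842 × 0.2231/√0.417]² / (0.4943 − 0.2231)² = 22.1, rounded up to 23. Other scales and variance choices give 17.2 to 23.4.

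The stated 21 lies in that range. It is a PFS number and is used below only as a denominator.

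**2. Who is outside the matched set.** 40 − 21 = 19, and 19/40 = 47.5%. This is a maximum at the enrolment cap. It shrinks with lower enrolment or more matched transplants.

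**3. Where each treated patient appears, if the restriction covers organ response.**

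| Path | Organ measurement named before any transplant | Analysis |
|---|---|---|
| Matched transplant | 5.1 and 5.3 | Main analysis |
| Haploidentical transplant | 5.1 and 5.3, but 5.3 is not explicitly required before coming off study | Neither group |
| No transplant, continues drug (4.1.4) | 5.1, then 5.3 at completion, possibly as late as progression | Separate summary; organ response not named |
| No transplant, stops drug | 5.1 and 5.3 | Separate summary; organ response not named |

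**4. Precision.** For a mean change with a common standard deviation, or for a proportion, the standard error ratio is √(40/21) = 1.38, if all 40 have a post-drug value. As an illustration only, take the 55% that Section 2.0 reports for a spleen volume reduction of at least 25% on MRI:
- 21 patients: √(0.55 × 0.45/21) = 10.9 points.
- 40 patients: √(0.55 × 0.45/40) = 7.9 points.

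**5. Direction of selection.** Assume 22 of 40 patients (55%) respond, and that responders reach matched transplant R times as often as non-responders. The proportion seen in the transplanted is 22R/(22R + 18):
- R = 0.5: 11/29 = 38%.
- R = 1: 22/40 = 55%.
- R = 2: 44/62 = 71%.

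The documents give no value of R, so the range 0.5 to 2 is an assumption.

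**6. What the restricted set alone can say.** If 12 of 21 respond and nothing is known of the other 19, the all-treated proportion lies between 12/40 = 30% and (12 + 19)/40 = 77.5%. This is a bound. It is not a forecast, because some of the 19 will have measurements.

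**The case against.** The strongest objection is that the restriction directly follows the sentence on tabulating safety parameters and may govern only those tables. That reading is possible. Two features favour the broader one: the primary analysis ends with the same sentence about its own analysis, and the next sentence sets aside more than safety data for patients not transplanted, which makes most sense if more than safety had been restricted. On the narrow reading no analysis set is stated for organ response, and the same wording is needed.

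A reader might infer that up to 19 patients have no usable organ score. The documents do not support that. The baseline and 5.3 measurements do not depend on transplant, and a separate summary is planned for those not transplanted. The 19 is the most that can fall outside the main analysis, not a count of unmeasured patients.

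A reader might also infer that the estimate is tilted towards responders. That is not shown either. Donor availability has no evident link to organ response. Patient choice could remove responders, who may prefer to stay on the drug under 4.1.4. Removal for progression or toxicity (7.1, 7.2) could act the other way. The statement in 2.0 is conditional and works through performance status, while enrolled patients already want transplant and meet performance and organ-function criteria (3.0). Under 4.1.5 they may proceed without completing 60 days of drug.

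Two further points stand. The plan has no response rate, so the percentages above illustrate selection and do not estimate its endpoint. And progression is only the latest point of completion for patients who continue; they may stop earlier for toxicity, non-compliance or withdrawal (7.0).

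**Conclusion.** The point holds as a mismatch between an endpoint measured before transplant and an analysis set defined by what follows. It rests on the broader reading of the closing restriction, which is the better supported of the two.

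The documented size is up to 19 of 40 treated patients (47.5%) outside the main analysis, with haploidentical recipients in no planned summary and no all-treated estimate. The loss of precision is a factor of up to 1.38 in the standard error. Bias is possible in either direction, and its size cannot be computed from the documents.

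This is more than missing detail, because a stated selection rule is applied to a drug effect. It should be corrected, but it concerns one descriptive secondary endpoint. PFS and its sample size do not change.

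**What to change.** In 6.0:
- Limit the closing restriction to transplant outcomes.
- State that change in liver and spleen size is analysed in all patients who took at least one dose of pacritinib and have a baseline measurement, whatever the later transplant or donor. Show the matched-transplant subset as supportive.
- Report how many patients lack a post-drug value, by path, and state the missing-data rule. One option is observed changes as the main summary, with a sensitivity analysis that sets missing changes to zero.

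In 5.0:
- State that patients leaving for a haploidentical transplant have the 5.3 organ measurement before they come off study, and include them.
- For patients who continue without transplant, record organ size at the physical examination of an existing monthly visit at a prespecified time, and use that value. The time should make duration on drug comparable with that of transplanted patients (4.1.2).

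The cost is an amendment to 5.2, 5.3 and 6.0 and a small amount of extra data recording; no added visits are needed for patients on drug. The reported change may be less favourable than in transplanted patients alone.
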